4. STUDY DESIGN

4.1 OVERALL DESIGN

An overview of the study design is provided in Section [1.2](#).

Study BP42698 is a 3-parallel arm (two dose levels of RO7049665 versus placebo), randomized, placebo-controlled, double-blind, event-driven, phase 2 study to assess efficacy of RO7049665 over placebo in patients with AIH in stable biochemical remission.

Two dose levels will be assessed, 3.5 mg RO7049665 (SC, Q2W) and 7.5 mg RO7049665 (SC, Q2W) and matching placebo.

This is an event-driven study, which means that participants stay in the study and on treatment until the participant experiences an event, the necessary number of events is reached, the participant stops for other reasons or withdraws consent, or the study ends.

All participants in the study will have been diagnosed with AIH previously and will have responded well to treatment with CCSs \pm NSIs. It will be the first attempt to taper out CCS completely *within the last 3 years* (see inclusion criteria Section [5.1](#)). At study entry, the disease status of the participants should allow for a stepwise removal of all

immunosuppressive treatment according to *local guidelines or practice*. If no local guidelines exist, EASL guidelines should be applied (EASL 2015: “Treatment should be continued for at least three years and for at least 24 months after complete normalisation of serum transaminases and IgG levels (biochemical remission). [...] In patients with continued histological disease activity (HAI >3), immunosuppressive treatment should not be discontinued, as relapse is almost certain to occur. [...] A trial of treatment withdrawal should be undertaken by stepwise reduction of immunosuppressive agents, and patients monitored closely.”). Participants will start with study treatment on Day 1 and start tapering CCS use from Day 8 onwards (see tapering schedule, Section 1.3, Table 3) to allow for complete CCS withdrawal within a maximum of 12 weeks, depending on the starting dose. Last dose of NSIs, if any, will be taken on Day –1.

Randomization in a 1:1:1 fashion will occur after patient eligibility is confirmed and before the first dose of study treatment is administered. Randomization will be stratified by equivalent prednisolone dose (≤ 7.5 mg daily versus > 7.5 mg daily or dual therapy [CCS any dose, plus NSI]).

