9. STATISTICAL CONSIDERATIONS

9.1 STATISTICAL HYPOTHESES

The hypothesis associated with the primary estimand (see Section 3.1) for this study is that the hazard ratio (HR) for the risk of relapse in the 7.5 mg RO7049665 compared with that of placebo is less than 1. In other words, that 7.5 mg RO7049665 increases the time to relapse following forced tapering of CCS/ \pm NSI therapy in participants with confirmed AIH who have been in stable biochemical remission for at least two years (*or less if according to the local practice*) and on stable AIH treatment for *at least 3 months prior to randomization (and who have not had a dose increase 6 months prior to randomization)*.

Six months after the start of CCS tapering, the relapse rate on placebo is assumed to be 45% (van Gerven 2013). It is estimated that treatment with RO7049665 will reduce the relapse rate to 15%. Under the assumption of exponential times to relapse, these six-month relapse rates imply mean times to relapse of 10.0 months in the placebo arm and 36.9 months in the treatment arm, leading to a reference hazard ratio of 0.272.

The hypotheses formally tested in this study are

$$H_0: HR = 1 \text{ vs } H_1: HR < 1$$

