9.2 SAMPLE SIZE DETERMINATION

The sample size for this study is based on independent pairwise comparisons of each RO7049665 group—i.e., high dose (7.5 mg) and low dose (3.5 mg) with placebo. The total sample size required is obtained by multiplying the appropriate per-group size by three. Methods for the control of the family-wise error rate are described both in this section and in Section 9.3.

The reference treatment effect is 0.272. The study will use an overall one-sided type 1 error rate (significance level) of 2.5%. A power of 90% against the reference treatment effect is required.

There will be one opportunity to stop for success before the end of the study, at 50% information. An O'Brien-Fleming-like alpha-spending rule will preserve the type 1 error rate. The success boundary will be binding.

There will be two opportunities to stop for futility before the end of the study: once at 25% information (i.e., when 25% of the maximum number of events have occurred) and once at 50% information (i.e. when 50% of the maximum number of events have occurred). A Pocock-like beta-spending rule will preserve power of the study. The futility boundary will be non-binding.

If the proportional hazards assumption holds, these assumptions imply that 29.1 events (i.e., 30 events for all practical purposes) in the placebo and 7.5 mg RO7049665 arms combined are required to achieve the desired power and significance levels.

Under the assumption that recruitment to the study will take approximately 19 months, that sites will be activated at uniform rate for six months, after which recruitment will plateau, and that follow-up should continue for at most 6 months after the last patient to enter the study is randomized, then recruitment of 28 participants per arm will generate the required number of events.

Table 9 Summary of the Group Sequential Design

Stage	Interim 1	Interim 2	End of study
Information rate	25%	50%	100%
Efficacy boundary (z-value scale)	∞	2.963	1.969
Futility boundary (z-value scale)	-0.046	0.738	
Number of subjects ^{a,c}	31	47	56
Cumulative number of events ^a	7.3	14.5	29.1
Analysis time ^{b,c}	11.7	16.3	25.0
Cumulative alpha spent	<0.0001	0.0015	0.025
Cumulative power	<0.0001	0.3159	0.9000
One-sided local significance level	N/A	0.0015	0.0245 ^d
Efficacy boundary (t)	N/A	0.211	0.482
Futility boundary (t)	1.035	0.679	
Overall exit probability (under H0)	0.4815	0.3136	
Exit probability for efficacy (under H0)	<0.0001	0.0015	

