Exit probability for efficacy (under H1)	<0.0001	0.3159	
Exit probability for futility (under H0)	0.4815	0.3121	

- a: For the two arms (the placebo arm and one of the RO7049665 arms) in question.
- b: Months after FPFV.
- c: Estimate.
- d: The hazard ratio that gives rise to a p-value of 0.0245 at the end of study analysis is approximately 0.594. This is the minimum detectable difference for the study and, assuming a mean time to relapse of 10.0 months in the placebo arm, corresponds to a mean time to relapse of 16.9 months on RO7049665.

Thus, the study is expected to recruit $3 \times 28 = 84$ participants in total and run for no longer than 25 months from FPFV to LPLV. If the enrolment rate or event rate differ from the assumptions used in these calculations, then either the number of participants or the duration of follow-up (or both) may be varied in order to ensure that the required number of events is observed.

Sample size calculations were performed using R package version 2.0.6 ([Wassmer and Pahlke, 2019](#)). Details are filed in the study electronic Trial Master File (eTMF).

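### Table 9's 31.6% chance of success at Interim 2, and to a lesser degree its 90% power, come from a normal approximation that is too optimistic at a hazard ratio of 0.272 with so few events

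*Combined protocol and SAP*

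**What the plan says.** Section 9.1 sets the assumptions: "Six months after the start of CCS tapering, the relapse rate on placebo is assumed to be 45" per cent, and "It is estimated that treatment with RO7049665 will reduce the relapse rate to 15" per cent. Exponential times then give means of 10.0 and 36.9 months. Section 9.2 continues: "The reference treatment effect is 0.272"; "The study will use an overall one-sided type 1 error rate (significance level) of 2.5" per cent; "A power of 90% against the reference treatment effect is required".

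Section 9.2 concludes that "these assumptions imply that 29.1 events (i.e., 30 events for all practical purposes") are needed in the placebo and 7.5 mg arms combined (the pair, below), with 28 participants per arm. Table 9 gives efficacy boundaries z = 2.963 at 50% information and 1.969 at the end, and futility boundaries z = -0.046 and 0.738. It gives cumulative power of 0.3159 at Interim 2 and 0.9000 at the end. The row headed "Exit probability for efficacy (under H1") repeats the 0.3159.

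Three other statements matter:
- The futility boundary is non-binding (Sections 4.1.2 and 9.2).
- The looks are triggered by 12, 23 and 45 events in the whole study, as a blinded stand-in for the pair's events (Section 9.6).
- The analysis is a Cox model (Section 9.5.2.1). The text does not say whether the statistic compared with the z boundaries is a score (log-rank), likelihood-ratio or Wald statistic.

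The documents describe no simulation check. Calculation details are said to be filed in the trial master file.

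**The concern.** Table 9 treats the log hazard ratio as normal with variance 4/events, which is accurate when the effect is modest and events split roughly evenly between arms. Neither holds here. At a hazard ratio of 0.272 and before any depletion of the placebo arm, the active arm contributes a share of 0.272/1.272 = 0.214, or about 3 of 15 events. By 30 events the split in simulation is about 9 to 21.

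An error of this kind matters most at Interim 2, where about 15 events must clear z = 2.963. The 0.3159 is the sponsor's stated chance of stopping early for success, and 90% is the stated design requirement. If both are too favourable, planning rests on properties the design does not have. The unnamed test adds to this, because the three candidates differ sharply at 15 events with an uneven split.

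**Working it through.** **1. Inputs.** Six-month relapse 45% and 15% (Section 9.1); one-sided 2.5%, boundaries, 28 per arm, 19-month accrual with a six-month ramp (Section 9.2 and Table 9); 1:1:1 allocation, so 1:1 within the pair (Section 4.1); triggers 12/23/45 (Section 9.6).

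**2. Reproducing the plan.**
- Hazards: -ln(0.55)/6 = 0.0996 and -ln(0.85)/6 = 0.0271 per month. The ratio is 0.2718 and |ln HR| = 1.3025.
- Expected z under the approximation: (√D/2) × |ln HR|, with D the pair events.
- Interim 2, D = 29.1/2 = 14.55: (3.814/2) × 1.3025 = 2.484. P(Z > 2.963 - 2.484) = P(Z > 0.479) = 0.316, the stated figure.
- Final, D = 29.1: expected z = 3.51. With Table 9's boundaries and futility followed, power is 0.900.
- At 30 events the same approximation gives power 0.908 and early success 0.330.

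Table 9 is therefore reproduced; the calculation was carried out correctly for the method chosen.

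**3. Simulating the same design.** The pair was simulated with exponential times, 28 per arm, the stated accrual, no dropout, an unadjusted treatment comparison and Table 9's boundaries. Looks were at 8/15/30 pair events (two thirds of 12/23/45, rounded), with 60,000 trials. Monte Carlo standard error is at most 0.2 points.

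| Test | Success at Interim 2 | Power, futility followed | Power, futility overruled |
|---|---|---|---|
| Table 9 | 31.6% | 90.0% | not given |
| Log-rank | 24.8% | 88.7% | 92.8% |
| Likelihood-ratio | 26.5% | 88.6% | 92.7% |
| Wald | 6.8% | 88.1% | 92.1% |

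Further runs of the log-rank case gave 24.6 to 25.2% early success. With looks at 7/15/29 events, closer to the 29.1 in Table 9, power is 87.1% (log-rank), 87.0% (likelihood-ratio) and 86.5% (Wald). Under no effect with futility ignored, rejection was 2.7%, 2.6% and 2.4% (30,000 trials), so the boundaries hold the type 1 error approximately.

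**4. Why the gap arises.** The simulated mean final log-rank z at 30 events is 3.40, against (√30/2) × 1.3025 = 3.57 under the approximation. The Freedman form, √30 × (1 - 0.2718)/(1 + 0.2718) = 3.14, errs the other way: it would give 83.0% power. The Wald test loses most at Interim 2 because its standard error grows with imbalance. A 3:12 split gives roughly √(1/3 + 1/12) = 0.645, against √(4/15) = 0.516 for an even split.

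**5. Events that would match the stated figures.** Power of about 90% with futility followed needs about 32 pair events (90.1%, 90.0% and 89.7% for log-rank, likelihood-ratio and Wald). Early success of 31 to 32% needs about 17 pair events at Interim 2 with log-rank or likelihood-ratio.

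**6. The actual triggers.** The factor 45/30 = 1.5 implies 15 events in the 3.5 mg arm. That is between the roughly 9 and 21 expected in the 7.5 mg and placebo arms, so it presumes an intermediate 3.5 mg effect. The documents give no separate figure for that effect, so it is varied here (three arms, futility followed, 30,000 trials per row).

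| 3.5 mg HR (assumed) | Mean pair events at looks | Power: log-rank / LR / Wald | Early success: log-rank / LR / Wald |
|---|---|---|---|
| 0.272 | 9.6 / 18.1 / 34.1 | 92.8 / 92.7 / 92.5% | 34.5 / 35.6 / 19.3% |
| 0.52 | 8.3 / 15.8 / 30.2 | 89.3 / 89.2 / 88.7% | 27.3 / 28.7 / 10.3% |
| 1 | 6.9 / 13.2 / 26.3 | 84.4 / 84.4 / 83.7% | 19.8 / 21.9 / 3.5% |

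**The case against.** The strongest reply has four parts.

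- **Table 9 contains no arithmetic slip.** This stands. It is a correct output of a standard group sequential calculation; the criticism is of the approximation's accuracy in this setting.
- **The power gap is small and futility is non-binding.** This stands too. At 30 pair events the loss is 1 to 2 points, rounding 29.1 up to 30 recovers part of it, and power exceeds 90% where the team overrules futility. A reader might infer that the trial is underpowered and needs more participants, or that 90% is reached only by ignoring futility. The documents support neither: with futility followed at the actual triggers, power is about 93% if both doses have a hazard ratio of 0.272.
- **The shortfall depends on the 3.5 mg arm.** This is correct, and it means one replacement figure would mislead as 0.3159 does. It does not rescue Table 9, which states its figures at its own event counts of 14.5 and 29.1.
- **The 7% figure presumes a Wald p-value.** It does. A reader might set 7% beside 31.6% and conclude that the figure is wrong more than fourfold. Section 9.5.2.1 names a Cox model but not a Wald test, so 7% is only what one permitted reading would give.

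It is also true that no decision rule uses the early-success probability and that Section 9.6 allows boundaries to be re-derived at the actual information. That limits the consequence to what the sponsor believes about the design.

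**Conclusion.** The point holds in a limited form. At the event counts Table 9 uses, its 0.3159 is too favourable by about 5 to 7 points with a log-rank or likelihood-ratio test (25 to 27%), and by about 25 points if a Wald test is used. Its 0.9000 is too favourable by 1 to 2 points at 30 pair events and by about 3 points at 29; alone, that would be minor. At the whole-study triggers the log-rank values run from about 93% power and 34% early success down to 84 to 85% and 20% as the 3.5 mg hazard ratio goes from 0.272 to 1.

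These figures assume exponential times, no dropout or censoring intercurrent events (the plan quantifies neither), a treatment-only comparison without the planned covariates, and Table 9's boundaries without re-spending. Approximately re-deriving the futility bounds at 30 events changes power only to 87.6 to 88.1%. The calculation file was not available and may contain checks the documents do not mention.

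**What to change.** In Section 9.2 and Table 9:

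1. Name the statistic compared with the z boundaries, and make Section 9.5.2.1 agree. The choice matters at Interim 2 far more than at the end.
2. Replace 0.3159, in both the cumulative power row and the efficacy exit row under H1, and the final 0.9000 with values simulated using that test.
3. Report them at the 12/23/45 triggers across stated 3.5 mg effects. With log-rank and futility followed: about 93% power and 34% early success at a hazard ratio of 0.272, about 89% and 27% at 0.52, and about 84 to 85% and 20% at 1. State the no-dropout and unadjusted assumptions.
4. Add that at 30 pair events power is about 88 to 89% if the futility boundaries are followed and about 92 to 93% if they are overruled.

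Keep the sample size. The cost is a few hours of simulation and slightly less favourable stated figures; no participants are added and the boundaries are unchanged.

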9.6 INTERIM ANALYSES

Formal interim analyses form an integral part of the analytical strategy for this study and are defined in Section 9.2. During the conduct of each interim analysis, the study team will remain blind to the results of the interim analysis. The interim analysis will be conducted by the statistician who is a member of the study IMC and independent from the study team and its results reviewed by the IMC as a whole.

It is unlikely that the interim (or final) analyses will be conducted precisely at the information fractions assumed in the sample size calculation. In this case, the stopping boundaries for both success and futility will be adjusted to take account of the actual information fractions at which the interim (and final) analyses were actually conducted while at the same time protecting the overall type 1 and type 2 errors of the study.

A further complication is that the planned timing of each interim analysis depends on the number of relapses observed in the 7.5 mg RO7049665 and placebo groups combined. This is a double-blind, three-arm study, so this number cannot be known without breaking the blind on a regular basis. Therefore, the timing of the interims will be estimated by looking at the number of relapses in the study as a whole, with conduct of the interims and the final analysis when the total number of relapses is expected to be 1.5 times greater than the number of events given in Section 9.2; that is, when 12, 23, and 45 events have been observed in the whole study.

The IMC charter will describe the planned interim analyses in detail.

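### Table 9 footnote d puts the final significance threshold at a hazard ratio of 0.594; the same column of the table, and the planned 29.1 events, give 0.482

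*Combined protocol and SAP*

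**What the plan says.** Table 9 in Section 9.2 summarises the group sequential design for placebo against one RO7049665 arm. Its end-of-study column gives:

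- an efficacy boundary of 1.969 on the z scale;
- a "One-sided local significance level" of 0.0245, which carries footnote d;
- 29.1 cumulative events in the two arms;
- 0.482 in the efficacy-boundary row labelled (t).

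The text above the table agrees on the event count: "29.1 events (i.e., 30 events for all practical purposes) in the placebo and 7.5 mg RO7049665 arms combined are required".

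Footnote d then says: "The hazard ratio that gives rise to a p-value of 0.0245 at the end of study analysis is approximately 0.594". It adds "This is the minimum detectable difference for the study" and, taking a placebo mean of 10.0 months, that the value "corresponds to a mean time to relapse of 16.9 months on RO7049665".

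**The concern.** The 0.482 in the table and the 0.594 in the footnote claim to be the same quantity: the observed hazard ratio that just reaches one-sided p = 0.0245 at the final analysis. They cannot both be right, and the gap is far too wide for rounding or for the word approximately to cover.

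Footnote d is the only place where the protocol says in words how large an effect must be observed for the final result to be significant. If 0.594 is wrong, the error is in the favourable direction. A reader would conclude that an observed 41% hazard reduction is enough (1 − 0.594 = 0.406), whereas the tabulated boundary requires about 52% (1 − 0.482 = 0.518).

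**Working it through.** **Inputs.** From Table 9: z = 1.969 (final), 2.963 and 0.738 (interim 2), −0.046 (interim 1); events 29.1, 14.5 and 7.3. From Section 9.1: 45% relapse on placebo at 6 months, exponential times, reference hazard ratio 0.272. From Section 4.1: 1:1:1 randomization, so 1:1 within each pairwise comparison.

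**Step 1. Reproduce the table's own boundaries.** With equal allocation and D events, the hazard ratio (HR) corresponding to z is exp(−2z/√D).

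| Cell | z | D | Computed | Table 9 |
|---|---|---|---|---|
| Final, efficacy | 1.969 | 29.1 | 0.482 | 0.482 |
| Interim 2, efficacy | 2.963 | 14.5 | 0.211 | 0.211 |
| Interim 2, futility | 0.738 | 14.5 | 0.679 | 0.679 |
| Interim 1, futility | −0.046 | 7.3 | 1.035 | 1.035 |

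All four cells match. The table does not call the (t) rows hazard ratios, but this agreement shows that they are.

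**Step 2. Check the rest of the design.** The one-sided p at z = 1.969 is 0.0245, as stated. A normal-approximation simulation (4,000,000 runs, information 25/50/100%, the Table 9 boundaries, futility followed) at HR 0.272 and 29.1 events gives power 90.0%, also as stated. The footnote is the only item among those checked that does not fit. Subject numbers and analysis times were not re-derived.

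**Step 3. Look for an event count that gives 0.594.** Critical HR = exp(−2 × 1.969/√D):

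| D | Meaning | Critical HR |
|---|---|---|
| 29.1 | planned, two arms | 0.482 |
| 30 | rounded up, two arms | 0.487 |
| 45 | all whole-study events placed in the two arms | 0.556 |
| 56 | every participant in the two arms has an event | 0.591 |

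The 45 comes from Section 9.6 ("when 12, 23, and 45 events have been observed in the whole study") and serves here only as an upper limit. Solving for D: (2 × 1.969/ln 0.594)² = (3.938/0.5209)² ≈ 57.2 events, more than the 56 participants planned in the two arms. At 29.1 events, other conventions move further from 0.594 or barely move: reading 0.0245 as two-sided gives 0.434, z = 1.96 gives 0.484, the Freedman form gives 0.465, and unequal event splits (60:40 to 80:20) give 0.475 down to 0.40.

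**Step 4. The p-value that 0.594 produces.** z = −ln(0.594) × √D/2:

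- D = 29.1: z = 1.405, one-sided p = 0.080
- D = 30: z = 1.426, p = 0.077
- D = 45: z = 1.747, p = 0.040

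**Step 5. Translate to relapse times.** Placebo mean = −6/ln(0.55) = 10.04 months.

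- HR 0.594: 10.04/0.594 = 16.9 months; 6-month relapse 1 − 0.55^0.594 = 29.9%.
- HR 0.482: 10.04/0.482 = 20.8 months; 6-month relapse 1 − 0.55^0.482 = 25.0%.

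The stated 16.9 months follows from 0.594, so 0.594 is not a garbled digit: the wrong value was carried into a second figure.

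**Step 6. Could 0.594 be a detectable effect in the power sense?** If the true HR were 0.594, the Step 2 simulation gives power of about 25–26% with both futility stops followed and about 29–30% with them ignored (29.1 to 30 events). No usual power criterion would yield that value either.

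**The case against.** The strongest reply is that nothing in the trial runs on this number. The correct 0.482 is printed in the same column, significance is decided by the alpha-spending boundary, and Section 9.6 recalculates the boundaries at the actual information fractions. That stands, and it limits the point to a misstated figure rather than a design flaw.

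A second reply is that 0.482 is not a fixed requirement. The final analysis is triggered by 45 events across three arms, so the two-arm count will vary. As an illustration, assume uniform accrual over 19 months, exponential times, no dropout and HR 0.272 for 7.5 mg. Then 45 total events put about 34 in the two arms if 3.5 mg is equally effective, and about 26 if 3.5 mg has no effect. Holding z at 1.969, the critical HR would be about 0.51 or 0.46. This is a fair reason to state the event count beside the threshold, but it does not bring 0.594 within reach.

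Third, the low power at a true HR of 0.594 is not itself evidence of error. Power is always modest at a critical value: at a true HR of 0.482 it is about 45% with futility followed. That is correct, and Step 6 is there only to rule out another reading of the footnote's label.

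Finally, the calculation details are filed in the electronic Trial Master File, which is not available here. Where 0.594 came from cannot be established from the documents.

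**Conclusion.** Footnote d is wrong as written. At the planned 29.1 events the hazard ratio giving one-sided p = 0.0245 is 0.482 (0.487 at 30 events), not 0.594. The matching mean time to relapse is about 20.8 months, not 16.9, and the matching 6-month relapse rate is 25.0%, not 29.9%. An observed 0.594 would miss significance clearly, with p = 0.080 against a local level of 0.0245.

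This rests on the usual log-rank approximation with 1:1 allocation, which the table itself uses, and on the protocol's exponential assumption for the conversion to months. It should be corrected because it misstates, in the trial's favour, what the final analysis could declare significant. Confidence is high.

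**What to change.** Replace footnote d with wording along these lines:

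> With 29.1 events in the two arms, a one-sided p-value of 0.0245 at the final analysis corresponds to an observed hazard ratio of about 0.482 (0.487 with 30 events). This is the largest observed hazard ratio, that is, the smallest observed effect, that would be statistically significant. With exponential times and a placebo mean of 10.04 months, it equates to a mean of about 20.8 months on RO7049665.

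Giving the placebo mean as 10.04 lets the division work from the stated input: the rounded 10.0 gives 10.0/0.482 = 20.7. Dropping the minimum-detectable-difference label avoids confusion with an effect the trial is powered to detect. Labelling the (t) rows of Table 9 as hazard ratios would also help.

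The cost is one corrected footnote. The stated threshold becomes less favourable; sample size, boundaries and conduct do not change.
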